2.1 Primary estimands

The primary clinical question of interest is: What is the effect of the ARNI versus ACEI/ARB on change on VA and ICD or CRT-D shocks and ATP in patients with implanted ICD or CRT-D?

The justification for the primary estimand is that it will capture both the effect of the study drug and the effect of additional medications, mirroring the conditions in clinical practice. Further details can be found in Section 12.

The primary estimand is described by the following attributes:

- 1. Population: patients defined through appropriate inclusion/exclusion criteria to reflect the targeted patient population for approval. Further details about the population are provided in Section 5.
- 2. Variable: VA, ICD and ATP events over 6 months of ACEI/ARB and 6 months of ARNI treatment.
- 3. Treatment of interest: ACEI/ARB for 6 months and ARNI for 6 months. Further details about the investigational treatment and control treatment are provided in Section 6.

Handling of remaining intercurrent events:

- 1. Treatment discontinuations for any reason: ignore (treatment policy strategy).
- 2. Unforeseen change in the dose of allowed concomitant medications: ignore (treatment policy strategy).
- 3. Unforeseen change in the dose of the investigational treatment or the control treatment due to adverse event or other reason: ignore (treatment policy strategy).

The summary measure: Proportion of patients with VA, ICD and ATP events over 6 months of ACEI/ARB and 6 months of ARNI treatment

[figure not shown]

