Information about common side effects already known about the investigational drug can be found in the label. This information will be included in the patient informed consent and should be discussed with the patient during the study as needed. Any new information regarding the safety profile of the investigational drug that is identified between label updates will be communicated as appropriate, for example, via an investigator notification (IN) or an aggregate safety finding. New information might require an update to the informed consent and then must be discussed with the patient. In the event of recollection of informed consent is needed, the Investigator may conduct the informed consent discussion remotely (e.g., telephone or video conference). Guidance issued by local regulatory bodies, and ECs/IRBs on this aspect prevail and must be implemented and appropriately documented (e.g., the presence of an impartial witness, sign/dating separate ICFs by trial participant and person obtaining informed consent, etc.).

Women of childbearing potential must be informed that taking the study treatment may involve risks to the fetus if pregnancy were to occur during the study and agree that in order to participate in the study they must adhere to the contraception requirements.

Male patients must be informed that if a female partner becomes pregnant while he is enrolled in the study, contact with the female partner will be attempted to request her consent to collect pregnancy outcome information.

8 Visit schedule and assessments

The Assessment Schedule (Table 8-1) lists all of the assessments when they are performed. All data obtained from these assessments must be supported in the patient's source documentation.

Patients should be seen for all visits/assessments as outlined in the assessment schedule (Table 8-1) or as close to the designated day/time as possible. Missed or rescheduled visits should not lead to automatic discontinuation.

Patients who discontinue from the study treatment are to complete the end of treatment visit as soon as possible, and attend the follow-up visits as indicated in Table 8-1.

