9.1 Discontinuation and completion

9.1.1 Study treatment discontinuation and study discontinuation

Discontinuation of study treatment for a patient occurs when study treatment is stopped earlier than the protocol planned duration, and can be initiated by either the patient or the investigator.

The investigator must discontinue study treatment for a given patient if, he/she believes that continuation would negatively impact the patient's well-being.

Discontinuation from study treatment is required under the following circumstances:

- 1. Patient/guardian decision
- 2. Pregnancy
- 3. Use of prohibited treatment as per recommendations in the prohibited treatment section
- 4. ACEI/ARBs daily dosage below guided dosage last for 1 month
- 5. Any situation in which study participation might result in a safety risk to the patient
- 6. Withdrawal of informed consent

Study treatment may be discontinued at the investigator's discretion if any of the following occurs:

- 1. Any severe, or suspected AE, that may jeopardize patient well-being, if the study drug is continued
- 2. Suspected occurrence of angioedema
- 3. Serum potassium >6.0 mmol/L at follow Visit
- 4. Any laboratory abnormalities that in the judgment of the investigator, taking into consideration the patient's overall status, prevents the patient from continuing participation in the study

If discontinuation of study treatment occurs, the Investigator should make a reasonable effort to understand the primary reason for the patient's premature discontinuation of study treatment and record this information.

Patients who discontinue study treatment or who decide they do not wish to participate in the study further should NOT be considered withdrawn from the study UNLESS they withdraw their consent (see withdraw of informed consent section). Where possible, they should return for the assessments indicated in the assessment schedule. If they fail to return for these assessments for unknown reasons, every effort (e.g. telephone, email, letter) should be made to contact the patient/pre-designated contact as specified in the lost to follow-up section. This contact should preferably be done according to the study visit schedule. Patients are to be discontinued from the study treatment if patient has not received the study treatment for > 14 days.

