12.1 Analysis sets

The Enrolled Set comprises all patients who enrolled into this study.

The Full Analysis Set (FAS) comprises all patients to whom study treatment has been assigned and who received at least one dose of study treatment. Patients will be analyzed according to the treatment they have been assigned to. Efficacy variables will be analyzed based on the FAS as the primary population.

The Safety Set (SAF) includes all patients who received at least one dose of study treatment. Patients will be analyzed according to the study treatment received. The safety population will be used for the analyses of safety variables.

The Per Protocol Set (PP) includes all patients in the FAS and have no major protocol deviations. PP population will be used for efficacy analysis.

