3.4 Interim analyses

The interim analysis (IA) and endpoint analysis will be performed in this study. An interim analysis will be performed when half of the required sample size (110 patients) have completed the 12-month treatment and follow-up period or prematurely withdrawn from study after at least one ARNI treatment, aiming at analyzing the study endpoints and safety, as well as re-evaluating the minimum sample size required.

For this interim analysis, the efficacy analysis will include efficacy data from 117 eligible subjects (i.e., subjects who have used ARNI at least once before freezing of the interim analysis data and completed the trial or early withdrawn).

Other analyses include all data from these 117 subjects and all subjects enrolled before these subjects.

4. Study Endpoints

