4.4 Past and concomitant medication and concurrent treatment

The CRF collects the drug name, total daily dose and unit, frequency of administration, route of administration, start date, end date, ongoing or not, and indication for prior and concomitant medications.

The CRF collects the name, start date, end date, ongoing or not, and indication of concomitant treatments (non-drug concomitant treatments, including surgery).

4.5 **Protocol Deviation and Medication Compliance**

Protocol deviations will be recorded by the clinical monitor.

Medication compliance for ACEI/ARB and ARNI is defined as: total actual dose/total planned dose *100%. Overall medication compliance for ACEI/ARB and ARNI will be summarized.

5. Statistical Hypotheses

For details, see section 7.4 Efficacy Analysis.

6. Analysis Datasets

The analysis data sets of this study are as follows.

Screened set

It includes all subjects who have signed the informed consent form.

Safety Analysis Set, SS

It includes all subjects who had received at least one dose of study treatment. Analyses will be performed according to the study treatment received. The safety analysis set will be used for all analyses except the efficacy analysis.

Efficacy Analysis Set

It includes SS subjects who have received ARNI at least once and completed 12 months of complete treatment and follow-up or who have early withdrawn from the study after receiving ARNI at least once. The efficacy analysis set will be used as the primary population to analyze the efficacy variables.

Per Protocol Set, PPS

It includes subjects in efficacy analysis set who had no major protocol violations, and the PP population will be used for efficacy analysis.

7. Statistical Methods

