7.4 Efficacy Analysis

7.4.1 Efficacy analysis of primary endpoint

The analysis will be based on the efficacy analysis set and the per protocol set.

- Proportion of paired patients who developed at least one SVT over 6 months of ACEI/ARB and 6 months of ARNI treatment.
- Paired proportion of patients by the occurrence of at least one NSVT over 6 months of ACEI/ARB and 6 months of ARNI treatment.
- Paired proportion of patients by the occurrence of at least one PVC over 6 months of ACEI/ARB and 6 months of ARNI treatment.
- Paired proportion of patients by the occurrence of at least one ICD or CRT-D shock over 6 months of ACEI/ARB and 6 months of ARNI treatment.
- Paired proportion of patients by the occurrence of at least one ATP event over 6 months of ACEI/ARB and 6 months of ARNI treatment.

Different hypothesis testing will be done on different types of variables:

Analysis of paired patient proportion

Occurrence events to be considered are SVT, NSVT, PVC, ICD or CRT-D shocks and ATP.

For each of the occurrence event, number of patients with at least one event stratified by treatments, will be presented in a 2×2 contingency table as follow:

ARNI (case)	ACEI/ARB (control)		
	At least one event	No event	Total
At least one event	a	b	a + b
No event	С	d	c + d
Total	a + c	b + d	N = a + b + c + d

Table 5-1 Matched pairs 2 × 2 contingency table

The following statistical hypothesis under 95% significance level will be tested to address the primary objective:

Null hypothesis: $p_b = p_c$ versus alternative hypothesis: $p_b \neq p_c$, where p_b and p_c are b/N and c/N, respectively. The test statistic considered is McNemar Test statistic as follow:

$$\chi^2 = \frac{\left(b-c\right)^2}{b+c}$$

which has a chi-squared distribution with degree of freedom of one.

However, an exact test (binomial sign test) will be used if the discordant cells have low values (b + c < 25).

Supportive analyses

In addition to the primary analysis, all the paired proportion will also be analyzed using the Liddell's exact test (Liddell 1983) as supportive analysis. From Table 5-1, the maximum likelihood estimate of relative risk (Mantel and Haenszel 1959), \hat{R} is given as follow:

$$\widehat{R} = \frac{b}{c}$$

Null hypothesis: $\hat{R} = 1$ versus alternative hypothesis: $\hat{R} \neq 1$ The test statistic considered, *F* is given as follow:

$$F = \frac{b}{c+1}$$

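### Read literally, the SAP's primary efficacy set omits patients who stop ARNI but stay in follow-up, which conflicts with the treatment-policy estimand

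*SAP*

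**What the plan says.** SAP section 6 (Analysis Datasets) builds the Efficacy Analysis Set from safety-set patients who have "received ARNI at least once and completed 12 months of complete treatment and follow-up or who have early withdrawn from the study" after at least one ARNI dose. It then gives the set its role: "The efficacy analysis set will be used as the primary population to analyze the efficacy variables". SAP 7.4.1 runs the primary test on two sets only: "The analysis will be based on the efficacy analysis set and the per protocol set". The per protocol set is nested in the efficacy set.

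The protocol is set up differently:

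- **Estimand (2.1):** "Treatment discontinuations for any reason: ignore (treatment policy strategy").
- **Full Analysis Set (12.1):** it "comprises all patients to whom study treatment has been assigned and who received at least one dose of study treatment". It has no completion condition.
- **Status after stopping treatment (9.1.1):** these patients "should NOT be considered withdrawn from the study UNLESS they withdraw their consent".
- **Visits after stopping treatment (section 8):** "Patients who discontinue from the study treatment are to complete the end of treatment visit as soon as possible, and attend the follow-up visits".

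SAP 3.4 describes the interim population in two ways. Its trigger counts patients who "have completed the 12-month treatment and follow-up period or prematurely withdrawn from study after at least one ARNI treatment". The next paragraph asks only that patients used ARNI and either finished the trial or left early, and does not mention completing treatment.

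**The concern.** The SAP definition offers two ways in: complete both treatment and follow-up, or leave the study. The protocol has a third group, patients who stop the drug and stay under observation. As written, someone who leaves altogether after one ARNI dose is in the set, while someone with device records through Month 12 but an incomplete ARNI course is not.

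A treatment-policy estimand needs exactly that third group. If they are left out, the population tested is not the one the estimand describes. The complete-case rule in Protocol 12.4.4 may also drop early leavers from the paired test, so the pairs actually analysed could be mostly treatment completers. Protocol 12.4.5 and 12.4.6 plan no sensitivity or supplementary analysis, so nothing else in the plan would show the difference.

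**Working it through.** **1. Apply the definition to a test patient.** The patient takes ARNI from Month 6, stops in Month 8, and attends Months 9 and 12.

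- First route (12 months of complete treatment and follow-up): not met, because treatment is incomplete.
- Second route (early withdrawal from the study): not met, because under Protocol 9.1.1 the patient has not withdrawn unless consent is withdrawn.
- Protocol Full Analysis Set: met.
- Estimand: the stop is to be ignored, so the patient belongs in the analysis.

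**2. Reproduce the plan's sample size.** Inputs from Protocol 12.8.1 and SAP 3.2.1: SVT in 8/120 patients on ACEI/ARB and 1/120 on ARNI, power 0.80, alpha 0.05, dropout 20%. SAP 7.1 makes tests two-sided.

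- ACEI/ARB-only: (8/120)(119/120) = 0.0661
- ARNI-only: (1/120)(112/120) = 0.0078
- Sum 0.0739 and difference 0.0583, as stated in the plan
- Power of the two-sided exact (sign) test, enumerated over the number of discordant pairs: 0.802 at N = 175, and 175 is the smallest N that reaches 0.80
- 175/0.8 = 218.75, so 219

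Both of the plan's figures reproduce.

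**3. How many pairs carry the SVT test.** At N = 175:

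- ACEI/ARB-only: 175 × 0.0661 = 11.6
- ARNI-only: 175 × 0.0078 = 1.4
- Total: 12.9

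This is below 25, so SAP 7.4.1 calls for the exact test. With 12 ACEI/ARB-only pairs, the two-sided exact p is:

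| ARNI-only pairs | p |
|---|---|
| 1 | 0.0034 |
| 2 | 0.013 |
| 3 | 0.035 |
| 4 | 0.077 |

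**4. Range under stated assumptions.** The documents give no rate of stopping ARNI while staying in follow-up. Assume a share s of the 175 pairs, and consider two cases. In case A these patients have no ARNI benefit: SVT risk is 8/120 in each period, so each discordant cell is (8/120)(112/120) = 0.0622. The difference with them included is then (1 − s) × 0.0583. In case B they respond like everyone else.

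| s | Patients | A: difference if included | A: power if included | B: N if omitted | B: power if omitted |
|---|---|---|---|---|---|
| 5% | 9 | 0.0554 | 0.72 | 166 | 0.77 |
| 10% | 18 | 0.0525 | 0.64 | 158 | 0.75 |
| 15% | 26 | 0.0496 | 0.56 | 149 | 0.71 |

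In case A, omitting them leaves the apparent difference at 0.0583, which overstates the treatment-policy effect. In case B, omission causes no bias and only costs sample size.

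**The case against.** The strongest reply is that this is loose drafting, not a planned exclusion. The second description in SAP 3.4 has no complete-treatment condition, and SAP 7.3.1 sorts patients only into those who completed the study and those who left early. On that split, someone who stops ARNI and attends Month 12 could count as a completer, and the clause would simply keep immature records out of the interim. This makes inclusion a possible reading, and the intent may well be innocent. It does not override the definition in section 6, and SAP 3.4 repeats the stricter treatment wording in its own trigger. In an open-label study, the choice between two readings of the primary population should not wait until outcomes are visible.

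A reader might go further and infer that the definition removes ARNI failures, or turns the primary test into an on-treatment comparison that favours ARNI. The documents do not support that. Patients withdrawn from the study for ablation (Protocol 6.2.1) or dose-limiting toxicity (6.5.2) after ARNI stay in the set through the second route. The reasons for stopping treatment in 9.1.1 include pregnancy, prohibited medication and patient decision. None is defined by arrhythmia, and nothing shows that patients who stop have more of it.

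Nor should the step from p = 0.0034 to p = 0.077 be read as a likely result. It needs three ARNI-only SVT patients among those omitted. For 9 to 26 patients that is a rate of 33% to 12%, against 6.2% even with no benefit. At 6.2% the expected number is 0.6 to 1.6, and the chance of three or more is about 2% (n = 9) to 22% (n = 26). Patients without benefit would on average add as many ACEI/ARB-only pairs. With 26 omitted, the other 149 give about 9.9 v 1.2, and adding the 26 back gives about 11.5 v 2.8, close to the 12 v 3 split with p = 0.035.

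One further limit stands. Protocol 9.1.1 asks for return visits only where possible, and its minimum data after a treatment stop cover treatments and adverse events, not device data. Widening the set alone would not secure complete pairs.

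**Conclusion.** The conflict holds as a matter of text. Read literally, the primary efficacy set omits patients who took ARNI, stopped it and remained in follow-up. The estimand and the protocol's Full Analysis Set both include them, and the only other efficacy set is nested inside the one that omits them.

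The number of such patients and the direction of any bias are unknown. The table shows what could be at stake: from lost sample size only, to a difference overstated by 0.003 to 0.009 (0.0583 against 0.0554 to 0.0496) if 5% to 15% of pairs are involved and have no benefit. Those shares and responses are assumptions. What follows from the plan's own figures is that about 13 discordant pairs carry the SVT test, so who enters the set should be settled before analysis.

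**What to change.** 1. **SAP section 6, final analysis:** define the Efficacy Analysis Set as all safety-set patients with at least one ARNI dose, whatever their later treatment status.
2. **SAP 3.4, interim:** keep a maturity condition, but base it on completing 12-month follow-up or leaving the study, not on completing treatment. Dropping the condition altogether would admit patients whose ARNI period is still running.
3. **SAP 7.4.1:** state that device data to Month 12 are used for patients who stop ARNI, where collected, and how a partial ARNI period is counted.
4. Leave any on-treatment selection to the per protocol set.

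The cost is a few sentences, with no new visits or procedures. The downside is small: some of the added patients may have incomplete device data and still fall out of the paired complete-case test, so their number should be reported.

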7.1 Overall Statistical Considerations

All statistical analyses are performed using SAS9.4.

All subjects related, efficacy related and safety related data should be collected and included in the statistical analysis. Notes or descriptive text records are only listed. For other data, descriptive statistical analysis would be performed, also statistical inference would be applied if needed.

In the statistical tabulations, screening number of subjects is the universal unique identifier of subjects in the study.

General rules of descriptive statistics: Quantitative variables are described by mean, standard deviation, standard error, median, minimum, maximum, Q1 and Q3. Categorical variables are

described by number and percentage of each category. Two-sided 95% confidence intervals will also be calculated for efficacy endpoints.

In the laboratory test part and the efficacy analysis part, 2 digits will be retained for the upper and lower limits of means and their confidence intervals, 3 digits for standard deviations, and 2 digits for medians, minimums, maximums, Q1 and Q3. In other parts, 1 digit more than the original values can be retained for the upper and lower limits of means and their confidence intervals, 2 digits more for standard deviations, and the original value digits for medians, minimums, maximums, Q1 and Q3. One decimal place will be retained for percentages and the upper and lower limits of their confidence intervals (but for efficacy analysis, 2 decimal places will be retained).

General principles of statistical inference: paired t test and Wilcoxon rank sum test will be used to compare quantitative data. McNemar test, exact test (binomial sign test) and Liddell's exact test will be used to compare categorical variables. All statistical tests will be subjected to twosided tests (unless otherwise specified), and a P-value less than or equal to 0.05 will be considered to indicate a statistically significant difference (unless otherwise specified).

For values such as "< xxx", half of the number following the less-than sign will be used to summarize and calculate statistics. For values such as "> xxx", xxx will be used to summarize and calculate statistics. For values such as "xx-xx", the average of the numbers before and after "-" will be used to summarize and calculate statistics. P value is rounded to 4 decimal places. If P < 0.0001, it is presented as '< .0001'; if P > 0.9999, it is presented as '> .9999'.

Baseline definition: Visit 1 data will be used as baseline of ACEI/ARB, and Visit 4 data as baseline of ARNI. If Visit 4 data are missing, the last available data before Visit 4 will be used.

Unless otherwise specified, the statistical description by visit only included the data of scheduled visits. For the evaluation involving maximum change, minimum change, abnormality, and clinically significant findings, the data of scheduled visits and unscheduled visits should be included.

Adverse events and medical history will be coded using MedDRA (see DMP for the specific version number).

Prior medications and concomitant medications will be coded using WHO Drug Dictionary (see DMP for the specific version number).

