8.4.1 Laboratory evaluations

Hematology, chemistry tests, NT-proBNP tests, Pregnancy Test (Table 8-3) will be measured by investigators' hospital lab at baseline, Month 6 and EOS. Clinically significant abnormalities must be recorded as either medical history/current medical conditions or AEs as appropriate.

Clinically notable laboratory findings are defined in Appendix 1.

The eGFR to determine eligibility of the patient for screening will be calculated at Visit 1 from the serum creatinine concentration by using the following formula (Stevens et al 2006):

eGFR (mL/min/1.73 m²) = 175 x (standardized S_{Cr} in mg/dL)^{-1.154} x (age in years)^{-0.203} x (0.742 if female), where S_{Cr} is the standardized serum creatinine value

The eGFR will also be measured at Month 6 and EOS in order to guide the investigator to take any appropriate action as necessary. Patient will be treatment discontinuation or suspend from the study if eGFR decrease > 50% of baseline value according to investigator decision.

Table 8-3	Laboratory Assessments
Test Category	Test Name
Hematology	Red blood cells count, white blood cells count, platelet count, hemoglobin, hematocrit, and WBC differential
Chemistry	Potassium, creatinine, glucose, sodium, chloride, calcium, blood urea nitrogen, total bilirubin, fractionated bilirubin (if total bilirubin >2x ULN), aspartate aminotransferase (AST), alanine aminotransferase (ALT), alkaline phosphatase, total protein, albumin, uric acid, lipid profile, hemoglobin A1C
Kidney function	serum creatinine
Biomarkers	NT-proBNP
Pregnancy Test	Serum/Urine pregnancy test

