8.4.2.1 Cardiac imaging

LVEF (%) and left ventricular end diastolic diameter (LVEDD) (mm) will be measured by echocardiography at baseline, Month 6 and EOS.

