8.4.2.2 Holter

Holter monitoring constantly records heartbeats for 24 hours and can detect arrhythmia events that might be missed by using the ECG. Data of Holter monitoring will be collected at baseline, Month 6 and EOS.

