12.5.2 Statistical model, hypothesis, and method of analysis

All the following analysis will be performed on the FAS and PP.

Analysis of change from date of treatment initiation after 6 months of treatment for paired quantitative endpoints

Variables involved are number of SVT experienced, number of NSVT experienced, number of hourly PVC experienced, number of ICD shocks experienced, number of ATP experienced and time duration of NSVT experienced.

For each variable, a summary table will be reported to show the changes from baseline to Month 3, and 6 post-indexing and changes from Month 6 to Month 9, and 12 post-indexing date. The changes will be summarized by mean, standard error, median, quartiles, minimum and maximum.

Amended Protocol Version 02 (Track changes)

The change from date of treatment in interested endpoint after 6 months of each treatment is calculated by taking the difference between value recorded at the date of first treatment intake and at the date of last treatment intake.

Normality will be checked for the changes calculated, if the data is parametric, paired t-tests will be performed; else if the data is non-parametric, Wilcoxon signed-rank test will be used.

Analysis of change from date of treatment initiation after 6 months of treatment for continuous endpoints

Variables involved are LVEF, NYHA and NT-proBNP.

For each variable, a summary table will be reported to show the changes from baseline to Month 3, and 6 post-indexing and changes from Month 6 to Month 9, and 12 post-indexing date. The changes will be summarized by mean, standard error, median, quartiles, minimum and maximum.

The change from date of treatment in interested endpoint after 6 months of each treatment is calculated by taking the difference between value recorded at the date of first treatment intake and at the date of last treatment intake.

Normality will be checked for the changes calculated, if the data is parametric, paired t-tests will be performed; else if the data is non-parametric, Wilcoxon signed-rank test will be used.

Other than that, the variables involved before and after the initiation of ARNI will also be analyzed using the same statistical method.

Note that NYHA is a qualitative variable, appropriate data transformation (to be described in Statistical Analysis Plan) will be used to convert it into quantitative form.

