7.5.3 Laboratory test results

The analysis is performed based on the SS.

From baseline, the quantitative laboratory tests results of each visit and their changes from baseline will be calculated and summarized in descriptive statistics. Pre-treatment and post-treatment laboratory test results are classified into abnormal with clinical significance, abnormal with no clinical significance, normal and not tested in an order of abnormal with clinical significance > abnormal with no clinical significance > normal > not tested, and then a shift table will be generated.

The listing for all abnormal findings in laboratory data will be provided.

7.5.4 12-lead ECG

The analysis is performed based on the SS.

The 12-lead ECG results and their changes from baseline are statistically described by visit.

The pre-treatment and post-treatment ECG results are classified in the order of abnormal with clinical significance, abnormal with no clinical significance, normal, not examined, and then a shift table will be generated.

12-Lead ECG results of all subjects will be listed.

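### When Visit 4 is missing, SAP 7.1 lets the pre-ACEI/ARB value serve as the ARNI baseline for LVEF, NT-proBNP, Holter and laboratory tests

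*SAP*

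**What the plan says.** SAP 7.1 assigns Visit 1 as the baseline for ACEI/ARB and Visit 4 as the baseline for ARNI. Its fallback reads: "If Visit 4 data are missing, the last available data before Visit 4 will be used". It sets no time limit and does not require the substitute to have been taken on ACEI/ARB. The next paragraph of SAP 7.1 says that, unless otherwise specified, "the statistical description by visit only included the data of scheduled visits". It then admits unscheduled visits for maximum and minimum change, abnormality and clinically significant findings.

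The schedule for the tests at issue is sparse:

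- Haematology, chemistry and NT-proBNP (Protocol 8.4.1): "hospital lab at baseline, Month 6 and EOS". The same section sets eGFR at Visit 1, Month 6 and EOS.
- LVEF and LVEDD (Protocol 8.4.2.1): "will be measured by echocardiography at baseline, Month 6 and EOS".
- Holter (Protocol 8.4.2.2): "Data of Holter monitoring will be collected at baseline, Month 6 and EOS".

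Protocol Table 8-1 agrees: these tests fall at Visits 1, 4 and 7 only.

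Protocol 12.5.2 obtains the change after six months of each treatment by "taking the difference between value recorded at the date of first treatment intake and at the date of last treatment intake". For LVEF, NYHA and NT-proBNP it adds that "the variables involved before and after the initiation of ARNI will also be analyzed using the same statistical method".

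**The concern.** A fallback to the last earlier value is reasonable when that value was taken under the same treatment, shortly before the switch. For the tests above no such value is scheduled. The rule reaches back about six months to Visit 1, so one measurement becomes the baseline of both treatments. Whatever happened on ACEI/ARB is then counted in the ARNI change, against the definition in Protocol 12.5.2.

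At stake are the ARNI change-from-baseline summaries for LVEF and NT-proBNP and their confidence intervals, and the before/after-ARNI test in Protocol 12.5.2. Mean-change summaries for laboratory tests, Holter and echocardiography are also at stake wherever the ARNI baseline is used. For laboratory tests, SAP 7.5.3 says "the quantitative laboratory tests results of each visit and their changes from baseline will be calculated and summarized in descriptive statistics", so a mean change in potassium, creatinine or eGFR that arose on ACEI/ARB could appear in an ARNI column.

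**Working it through.** The plan gives no figure for this point, so there is none to reproduce.

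**Which variables are exposed (Protocol Table 8-1)**

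| Variable | Scheduled visits up to Visit 4 | Fallback lands on |
|---|---|---|
| LVEF/echo, Holter, haematology, chemistry, NT-proBNP | 1, 4 | Visit 1 (ACEI/ARB baseline) |
| ECG | 1, 3, 4 | Visit 3 (on ACEI/ARB) |
| NYHA, vital signs, device data | 1, 2, 3, 4 | Visit 3 (on ACEI/ARB) |

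**Size of the shift**

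Let A be the mean change from Visit 1 to Visit 4, B the mean change from Visit 4 to Visit 7, and f the share of patients who start ARNI without a Visit 4 value. Missingness is taken as unrelated to the changes.

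- With a Visit 4 value, the ARNI change has mean B.
- Without one, it is Visit 7 minus Visit 1, with mean A + B.
- Over all patients: (1 − f)B + f(A + B) = B + fA. The shift is fA.

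**Effect on a before/after-ARNI t-test when B = 0**

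From Protocol 12.8: N = 175 evaluable patients, SD 15 and two-sided 0.05. The standard error without fallback is 15/√175 = 1.13.

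Assumed, because the documents give no value: f = 2%, 5% or 10%, and A = 3 or 6 LVEF points. The 3 is borrowed from the planned treatment difference in Protocol 12.8.2, which is not an estimate of first-period change. The SD of 15 is applied to both kinds of patient.

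SD of the mixture = √(225 + f(1 − f)A²). Noncentrality = fA/(SD/√175). The chance of false improvement is the upper-tail probability of the noncentral t with 174 degrees of freedom beyond 1.974.

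| f | A | Shift fA | SD | Noncentrality | False improvement |
|---|---|---|---|---|---|
| 2% | 3 | 0.06 | 15.006 | 0.053 | 2.8% |
| 2% | 6 | 0.12 | 15.024 | 0.106 | 3.2% |
| 5% | 3 | 0.15 | 15.014 | 0.132 | 3.4% |
| 5% | 6 | 0.30 | 15.057 | 0.264 | 4.5% |
| 10% | 3 | 0.30 | 15.027 | 0.264 | 4.5% |
| 10% | 6 | 0.60 | 15.108 | 0.525 | 7.5% |

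The nominal value is 2.5%. If A is negative, the shift has the same size but works against ARNI.

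**The paired comparison of period changes**

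A patient without Visit 4 also lacks the Month 6 ACEI/ARB result. SAP 7.2.1 imputes nothing unless otherwise specified, so that patient has no ACEI/ARB change and drops out of the pair. The fallback therefore does not enter this comparison.

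**The case against.** The strongest reply is that few patients are exposed. ARNI is dispensed at Visit 4 (Protocol 6.7 and Table 8-1), so a patient who starts ARNI has normally attended that visit. Only a skipped echocardiogram, Holter or blood draw triggers the fallback, apart from the home delivery or self-purchase that Protocol 6.7 allows during the pandemic. This stands, and it limits the size of the problem. It does not make the rule right, since the SAP itself provides for a missing Visit 4.

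A second reply is that the false-improvement figures join a SAP rule to a test that appears only in the protocol. This also stands. The readable text of SAP 7.4.2 compares values and changes between treatments with paired tests and does not carry over the before/after-ARNI test. The figures apply only if that test is run using the SAP baseline.

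A third reply is that the restriction to scheduled visits concerns by-visit description, not the baseline definition, so an unscheduled value between Visits 1 and 4 might count as the last available one. The SAP does not settle this. Even if such values count, patients without one still fall back to Visit 1.

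A reader might infer that the laboratory shift tables would show ACEI/ARB abnormalities as ARNI abnormalities. The documents do not establish this. SAP 7.5.3 classifies results as pre-treatment and post-treatment without naming the ARNI baseline, and SAP 7.1 admits unscheduled values for abnormality evaluations.

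**Conclusion.** The point holds as a narrow error in a stated rule, and it should be clarified. For tests scheduled only at Visits 1, 4 and 7, the fallback contradicts Protocol 12.5.2 and adds fA to the mean ARNI change. That is 0.15–0.6 LVEF points if 5–10% of values are missing and the first-period change is 3–6 points. If the protocol's before/after-ARNI t-test is run on such data, false improvement rises from 2.5% to about 3.4–7.5%; with 2% missing it is 2.8–3.2%. All of this rests on assumed missing rates and assumed first-period changes.

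Three stronger conclusions that a reader might draw are not supported:

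- That the primary result is distorted. The primary endpoints are yes/no occurrences within each period and use no baseline value.
- That the contrast between the two period changes is biased. It would move by 2fA (0.3–1.2 points on the same assumptions) only if Visit 1 also stood in for the Month 6 result, and the SAP does not say so.
- That missing ARNI-period data also leave the primary tables without a rule. Protocol 12.4.4 already sets a complete-case analysis, and nothing in the SAP overrides it.

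NYHA, ECG, vital signs and device data have a Visit 3 value, so the fallback is reasonable for them.

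**What to change.** In SAP 7.1, restrict the ARNI baseline fallback to values taken on ACEI/ARB after Visit 1 and before the first ARNI dose, and state that unscheduled values in that interval count. If there is none, leave the ARNI baseline missing. For each variable, report how many patients used a substitute value and how many have no ARNI baseline.

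With this rule a Visit 1 value can no longer serve as the ARNI baseline, so the fA term disappears. The cost is one sentence in the SAP and a few fewer patients in the ARNI change summaries. Sample size, visit schedule and primary analysis do not change.
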